9.3 Analysis Methods for the Primary Outcome

The mean change from baseline in UDI total score will be compared between groups at 6 months at the p<0.05 statistical significance level using a mixed effects analysis of covariance model for repeated measures (MMRM) with adjustment for baseline UDI score, and randomization stratification factors site and age group. The model will include fixed effect categorical factors for treatment group, visit (3 6 months, 9, 12), and treatment × visit interaction with an unstructured covariance pattern for the within-subject repeated measures separately within the two treatment groups. Estimates, p-values and 95% confidence intervals will be presented for treatment group comparisons at 6 moths (primary) and 3 months (secondary), and 9 and 12 months (other efficacy). (SM Davis, 2014)

Example code from SAS to produce this analysis is as follows:

```
proc mixed covtest;
    class subject site trtgp VISIT;
    model DELTA_VAR = BL_VAR site trtgp VISIT trtgp*VISIT / ddfm=kenwardroger;
    repeated VISIT / subject=subject type=UN group=trtgrp R rcorr;
    title "Mixed model for change from baseline";
    lsmeans trtgp*VISIT / cl pdiff=all;
run;
```

We will report whether change in total UDI score from baseline to 6 months is statistically significantly different between groups. If the difference is statistically significant, the potential clinical significance of the difference will be discussed. We recognize that our sample size may allow us to find a difference between groups that is statistically significant yet smaller than published MID for total UDI score for women with MUI. However, published MIDs were calculated based on populations that may be somewhat different from the one targeted for enrollment in MUSA, and an exploratory aim of MUSA is to explore whether the MID in this population differs from previously published values (see section 9.5.3).

Sensitivity analysis: This model assumes missing data due to a missed visit or early study discontinuation is missing at random (MAR). If more than 10% of participants are missing their 6-month score and a statistical difference is seen between groups at 5 months, then a sensitivity analysis in order to assess the robustness of the primary results to missing data will be performed using multiple imputation under a not -missing-at-random (NMAR) as follows: missing data from discontinuations in the arm found to be superior will be imputed based on data from the less superior arm ("control-based imputation"). (Ratitich et al 2013, 2,14). This sensitivity analysis essentially takes the conservative assumption that missing data after discontinuation in the superior arm have outcome values as if they were in the non-superior arm.

A supportive per-protocol analysis of the primary outcome will be based on the per-protocol population with data excluded (set value to missing) for any data points at 3 or 6 months that are collected after a cross-over treatment or additional therapy. Since crossing over and additional treatments were allowed after 6 months, data points after 6 months are not planned to be excluded in any sensitivity analyses.

Sensitivity of the per-protocol analysis: the data set to missing due to off-protocol treatments is assumed by the model to be missing at random. However, it is possible that if these measures were assessed without additional therapy, they might have reflected poor outcomes. To assess the impact of the results from the missing data, we will conduct a tipping point multiple imputation analysis, in which the missing values are increased (worsened) by a fixed value, in successive intervals across successive analyses until a point at which statistical interpretation of the p-value at 6 months between treatment groups is changed. (Ratitich et al 2013, 2,14).

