6.2.2 Primary Aim

Primary Outcome

The mean change from baseline in UDI total score will be compared between groups at 6 months at the $p<0.05$ statistical significance level using a mixed effects analysis of covariance model for repeated measures (MMRM) with adjustment for baseline UDI score, and randomization stratification factors site and age group. The model will include fixed effect categorical factors for treatment group, visit (3 and 6 months), and treatment \times visit interaction with a heterogeneous Toeplitz covariance pattern for the within-subject repeated measures. Estimates, p-values and 95% confidence intervals will be presented for treatment group comparisons at 6 months (primary) and 3 months (secondary).

This model assumes missing data due to a missed visit or early study discontinuation is missing at random. If more than 10% of participants are missing their 6-month score, then a sensitivity analysis will be performed using multiple imputation under a variety of missing data patterns to be specified in the statistical analysis plan in order to assess the robustness of the primary results to missing data. .

We will report whether change in total UDI score from baseline to 6 months is statistically significantly different between groups. If the difference is statistically significant, the potential clinical significance of the difference will be discussed. We recognize that our sample size may allow us to find a difference between groups that is statistically significant yet smaller than published MID for total UDI score for women with MUI. However, published MIDs were calculated based on populations that may be somewhat different from the one targeted for enrollment in MUSA, and an exploratory aim of MUSA is to explore whether the MID in this population differs from previously published values.

Secondary Outcomes

There are two secondary outcomes for the primary aim. The mean change from baseline in UDI-stress and UDI-irritative subscores will be compared between groups at 6 months. Each of these outcomes will be evaluated using an alpha level of 0.05, with no adjustment for multiple comparisons. The statistical analysis of the two secondary outcomes will be identical to the analysis described above for the UDI total score.

6.2.3 *Exploratory Aims*

All statistical evaluations of the exploratory aims are for descriptive purposes and p-values resulting from these analyses will not be evaluated for statistical significance.

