^a SD: standard deviation is estimated from ESTEEM participants with at least 4 Urge IEs/3 days using a repeated measures linear model for change from baseline to 3 and 6 months with adjustment for baseline value and clinical site.

^b Assumes 5% of randomized participants discontinue by 6 months estimated by average of ROSETTA and ESTEEM

Statistical Analysis and Feasibility

The analysis at 12 months will be similar to planned 6 month analysis. The primary MUSA study outcome remains at 6 months.

The discontinuation rate of ESTEEM and ROSETTA were 12% and 9%, respectively at 12 months. An additional participant incentive of \$75 will be given at the 12 month call. Given that MUSA participants are allowed to pursue other clinical treatments after 6 months, including the alternative arm treatment, retention

from 6 to 12 months should not exceed 10%. The 9 and 12 month calls will be halted if we determine that it is not feasible to collect sufficient data due to time or budget constraints

Statistical Analysis Plan

Primary outcome: The mean change from baseline in UDI total score will be compared between groups at 12 months at the $p<0.05$ statistical significance level using a mixed effects analysis of covariance model for repeated measures (MMRM) with adjustment for baseline UDI score, and randomization stratification factors site and age group. The model will include fixed effect categorical factors for treatment group, visit and treatment \times visit interaction with a heterogeneous Toeplitz covariance pattern for the within-subject repeated measures. Estimates, p-values and 95% confidence intervals will be presented for treatment group comparisons at 12 months.

This model assumes missing data due to a missed visit or early study discontinuation is missing at random. If more than 10% of participants are missing their 12-month score, then a sensitivity analysis will be performed using multiple imputation under a variety of missing data patterns to be specified in the statistical analysis plan in order to assess the robustness of the primary results to missing data.

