7.3 Handling of Dropouts and Missing Data

The repeated measures analysis for the primary outcome for the MITT population (see Section 9.3) assumes missing data due to a missed visit or early study discontinuation is missing at random. The impact of missing data on the primary efficacy MITT analysis results will be explored through multiple imputation sensitivity analyses using control-based imputation if more than 10% of participants in the mITT population are missing their 6-month UDI score and a treatment group difference is identified, in order to assess the robustness of the primary results to missing data. (See Section 9.3). Sensitivity analyses are not planned for secondary or other outcomes.

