7.4 Handling of Cross-over and off-study treatment

It is a protocol deviation for participants to receive any other UI treatments during the first 6 months after treatment. After 6 months, participants may cross-over to receive their non-randomized treatment and may also receive additional off-study UI treatments.

For all primary mITT analyses, data for participants who cross-over and receive the other study treatment or receive an off-study treatment during the first 6 months will be included in all analyses in an intent-to-treat fashion.

The mITT analysis is conservative as it may minimize differences between groups or bias results to make a treatment appear more efficacious due to inclusion of data after a participant has received the other study treatment or additional treatments. Therefore, a supportive per-protocol analysis of the primary and 3 secondary outcomes will be based on the per-protocol population with data excluded (value set to missing) for any data points at 3 or 6 months that are collected after a cross-over treatment or additional therapy. Since crossing over and additional treatments were allowed after 6 months, data points after 6 months will not be excluded. See Section 9.3.

The per-protocol analysis is expected to remove bias in outcome caused by the off-protocol additional therapies, in order to provide a more accurate estimate of the true difference in UDI 6 months after the randomized treatment with no further interventions.

The repeated measures analysis assumes that the values set to missing after cross-over treatment are missing at random. However, since additional treatment was sought, it's possible that the outcome scores with no extra treatment received, had they been available, would reflect poorer outcome scores than other recorded data, and thus not be missing at random. Therefore, a multiple imputation tipping point sensitivity analysis of the per-protocol analysis will be conducted. Tipping point analysis will consist of a set of multiple imputation analyses in which the imputed UDI change from baseline scores are increased (made worse) by successively fixed amounts, in order to identify at what amount would have a change in the interpretation of the per-protocol analysis. See Section 9.3

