13 CHANGES TO THE ANALYSIS PLANNED IN THE PROTOCOL

The primary repeated measures mixed model analysis planned in the protocol specified a heterogeneous Toeplitz covariance pattern for the within-subject repeated measures. The SAP updates this covariance pattern to instead be unstructured separately within each treatment arm. The unstructured pattern within group is preferable for the MUSA design since the Botox arm can receive a second treatment within the first 6 months but the sling arm does not, and additional treatments are allowed in either arm after 6 months. It is therefore best to specify the most general correlation structure possible.

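### The SAP makes the protocol's missing-data sensitivity analysis of the primary result depend on finding a treatment difference, drops the addendum's 12-month version, and lists neither change in Section 13

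*SAP*

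**What the plan says.** **Protocol, 6 months (6.2.2).** The trigger is missingness alone: "If more than 10% of participants are missing their 6-month score, then a sensitivity analysis will be performed using multiple imputation under a variety" of missing-data patterns. The patterns are left to the SAP. The trigger is not, and the stated aim is to test how robust the primary results are.

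**Protocol, 12 months (addendum, Statistical Analysis Plan).** The same rule applies: "If more than 10% of participants are missing their 12-month score, then a sensitivity analysis will be performed using multiple imputation under a variety" of patterns.

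**SAP, trigger.** Section 7.3 runs control-based imputation "if more than 10% of participants in the mITT population are missing their 6-month UDI score and a treatment group difference is identified". Section 9.3 has "If more than 10% of participants are missing their 6-month score and a statistical difference is seen between groups at 5 months". Section 7.3 names the mITT population but gives no time point for the difference. Section 9.3 gives a time point but no population.

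**SAP, method.** One only: "missing data from discontinuations in the arm found to be superior will be imputed based on data from the less superior arm".

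**SAP, other outcomes (7.3).** "Sensitivity analyses are not planned for secondary or other outcomes". Section 3.1.2 lists the 12-month comparison as an exploratory aim.

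**SAP, a different sensitivity analysis (7.4).** "a multiple imputation tipping point sensitivity analysis of the per-protocol analysis will be conducted". It depends on neither the 10% rule nor a significant result. Its stated reason is values set to missing after cross-over or additional treatment.

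**SAP 13, changes from the protocol.** One entry: "The SAP updates this covariance pattern to instead be unstructured separately within each treatment arm".

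**The concern.** The primary MMRM assumes that missing scores are missing at random. The protocol wanted that assumption tested once more than 10% of 6-month scores were missing, whatever the result. Under the SAP, a significant result is tested and a non-significant one is not. Yet participants are unmasked and the outcome is self-reported, so drop-out related to unseen scores could hide a difference as well as create one.

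The chosen method reinforces this. Imputing the superior arm from the other arm has no meaning when neither is superior, so deleting the extra condition would still leave nothing to run on a null result.

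Section 13 exists to show where the SAP leaves the protocol. A reader who relies on it would not learn that the trigger now depends on the result, or that the 12-month check has gone.

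**Working it through.** **1. The plan's own figures.** Inputs from SAP 6: difference 26, SD 46.5, power 90%, loss 5%; two-sided alpha 0.05 from SAP 7.8. The t-based calculation gives 69 per arm, and 69/0.95 = 72.6, so 73 per arm and 146 in total. These agree with the SAP, and no sample-size figure is in dispute.

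**2. Texts side by side.**

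| Item | Protocol | SAP |
|---|---|---|
| 6-month trigger | more than 10% missing | more than 10% missing **and** a treatment difference |
| Patterns | several, left to the SAP | one, which needs a superior arm |
| 12-month check | same rule as at 6 months | none |
| Listed in Section 13 | – | no |

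The SAP model uses the UDI at 3, 6, 9 and 12 months, so there is no 5-month score to test.

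**3. How often the 6-month trigger is met, on all randomised women.** More than 10% of 146 means at least 15. With independent losses, P(X ≥ 15), X ~ Binomial(146, p):
- p = 5% (plan): 0.7%
- p = 6.8% (ESTEEM sling arm, Protocol Table 10): 7.3%

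**4. The same on the mITT population.** SAP 5.1 excludes untreated women and those with no post-baseline efficacy data. The documents do not say what share of losses is of this kind. *Assume* a quarter. A woman in mITT then lacks the score with probability 0.75p/(1 − 0.25p), and I average over the binomial size of mITT:
- p = 5%: 0.0375/0.9875 = 3.8%, giving a trigger chance of 0.04%
- p = 6.8%: 0.051/0.983 = 5.2%, giving 0.8%

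Missed visits without discontinuation would raise these figures. The documents give no rate for them.

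**5. How often the added condition then cancels the check.** Read the difference as two-sided p < 0.05 at 6 months, with about 65 observed per arm. The chance of a non-significant result is about 11% if the true difference is 26, 20% if 23, 50% if 16, and 95% if there is none. Jointly with the trigger in step 3, for true differences from 26 down to 0, this is 0.08% to 0.6% at 5% loss and 0.8% to 6.9% at 6.8% loss.

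**6. What the cancelled check could show.** Take 15 missing. *Assume* that unseen scores in one arm are worse than the model predicts by 26 to 46.5 points (the MID to one SD).
- Losses even: 7.5/73 = 0.103, so the difference moves by 2.7 to 4.8 points.
- All losses in that arm: 15/73 = 0.205, so it moves by 5.3 to 9.6 points.

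With 65 and 66 observed, SE = 46.5 × √(1/65 + 1/66) = 8.13, and about 16.1 points are needed for significance. Only a null result already fairly close to that line could change.

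**7. 12 months.** Loss rates are 9% (ROSETTA, addendum), 10% (planned 5% + 5%) and 12% (ESTEEM, addendum). The chance of more than 10% missing is 33%, 50% and 78% on 146 randomised, and about 7%, 14% and 35% under the assumption in step 4. SAP 1 notes that two women left before the extension; they are not added here and would raise these figures.

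**The case against.** - **Control-based imputation guards against a false claim of superiority**, which suits the protocol's alternative hypothesis, and the protocol left the patterns to the SAP. This stands as a defence of the method. It does not defend the trigger, which was not delegated, and one pattern is not a variety.
- **The tipping-point analysis can start from a null result.** A reader might infer that a null result gets no missing-data check at all, and the documents do not support that. The analysis is ungated, and its wording does not clearly exclude ordinary drop-outs from the imputed values. But it belongs to the per-protocol analysis and is aimed at scores removed after off-protocol treatment, so it does not replace a check of the mITT result.
- **The 5 months is a typing slip.** Agreed: the same sentence refers to the 6-month score, and 7.3 has no such time point. A reader might infer a condition that can never be met; that reading should not be pressed. Correcting the number leaves the dependence on the result.
- **The 12-month comparison carries little weight.** It is exploratory, follows an observational period with cross-over allowed, and has descriptive p-values. SAP 7.3 states the general exclusion openly, and SAP 2 allows further exploratory analyses. All of this stands; what remains is that Section 13 does not list the change.
- **The trigger is rare and 146 is the wrong base.** Largely accepted: SAP 7.3 counts mITT, which is why both bases are shown.

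**Conclusion.** The mismatch is real and minor. SAP 7.3 and 9.3 narrow a protocol-required check of the primary result by making it depend on that result, and give no mITT method for a null finding. SAP 7.3 also removes the addendum's 12-month check through a general sentence. Section 13 declares neither.

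At 6 months this is a rarely triggered safeguard: 0.7% to 7.3% on all randomised women, or 0.04% to 0.8% if a quarter of losses fall outside mITT. Nothing here shows that the primary estimate is biased, and the documents would not support that inference. At 12 months the trigger is more likely to be met, but 33% to 78%, or about 7% to 35% under the same assumption, are ranges that depend on the denominator and not estimates. Because the SAP treats that comparison as exploratory, the 12-month part is a matter of disclosure and does not touch the main conclusion.

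The figures assume independent losses at the documents' rates. The one-quarter share is an assumption with no source in the documents.

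**What to change.** - In SAP 7.3 and 9.3, delete the treatment-difference condition, correct 5 months to 6 months, and give both sections the same population and wording.
- When more than 10% are missing, run a pre-specified mITT imputation analysis that needs no superior arm, whatever the p-value. Arm-specific delta adjustment or a tipping-point analysis would serve. The protocol does not prescribe a method, so this is one reasonable choice.
- Keep control-based imputation as an addition when one arm is superior.
- Restore the 12-month check, or state with a reason that it is dropped.
- Record every one of these departures from the protocol in Section 13.

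The cost is SAP wording and a few extra imputation runs. No new data, visits or participants are needed.

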6 SAMPLE SIZE DETERMINATION

MUSA will randomize 146 women to treatment with Botox or Sling in a 1:1 ratio. The sample size was derived to provide sufficient power for the primary Aim (comparison of Botox versus sling after 6 months) assessed for the primary outcome (change in UDI total score).

For the primary outcome (UDI total score change from baseline at 6 months), alpha was set at 0.05 and power was set at 90%.

Sample size estimates were based on an evaluation of minimum important differences (MIDs) and corresponding standard deviation (SD) for the UDI total score from the ESTEEM study of MUI, with support from other published populations of women with urge and stress incontinence; however, the populations on which those MIDs were based might differ from the target population of mixed incontinence for MUSA. Thus, our goal was to power the study to detect a statistically significant difference between groups in change from baseline in UDI total score at 6 months for the UDI MID determined from ESTEEM as that will be a clinically important difference in our population. To use the most accurate standard deviation applicable to MUSA, we calculated the SD based on a mixed effects repeated measures model with adjustment for baseline UDI score and clinical site rather than the SD of the observed data in order to account for improvements in variance estimation from the covariate adjustment planned for MUSA. To most closely match MUSA, this analysis model included all 3-month and 6-month ESTEEM data points after any retreatments and excludes patients with <4 Urge IEs/3 days. The MID for ESTEEM UDI-Total is 26, and the SD=46.5 from the analysis model, resulting in an effect size = 0.56.

Total number of randomized patients required to meet planned power estimates were adjusted for the assumed patient discontinuation rate at 6 months. Based on average estimates from ROSETTA and ESTEEM, we plan for 5% discontinuation rate by 6 months.

The evaluable sample size required at 6 months for 90% power for the primary total UDI outcome is 69 per arm. Because data from ROSETTA and ESTEEM suggests that follow-up at 6 months should be about 95%, a total sample size of 73 randomized per treatment arm is selected (69/0.95 =73), for a total sample size of 146 randomized participants.

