7.8 Multiple Comparisons and Multiplicity

The primary hypothesis will be tested at a nominal two-sided type I error of 0.05. The three secondary outcomes will also be tested at a nominal two-sided type 1 error of 0.05, with no adjustment for multiple comparisons, and thus p-values are descriptive. All p-values for any baseline and demographic characteristics, exploratory outcomes, and safety parameters will also be for descriptive purposes only.

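### The tipping-point analysis gives one series of worsening amounts for both arms, so its ability to overturn the per-protocol result depends on how the imputed values split between arms

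*SAP*

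**What the plan says.** The per-protocol analysis sets to missing "any data points at 3 or 6 months that are collected after a cross-over treatment or additional therapy" (SAP 7.4; SAP 5.2 and 9.3 say the same). This applies to either arm. The SAP accepts that these values may not be missing at random, because women who sought more treatment might have scored worse without it. It therefore plans a tipping-point analysis.

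- SAP 7.4 describes it as a set of multiple imputation analyses "in which the imputed UDI change from baseline scores are increased (made worse) by successively fixed amounts".
- SAP 9.3 describes it as one "in which the missing values are increased (worsened) by a fixed value, in successive intervals across successive analyses", continued "until a point at which statistical interpretation of the p-value at 6 months between treatment groups is changed".

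Neither section names an arm, allows a different amount in each arm, or sets a step or a maximum. Neither says whether ordinary missed visits are shifted along with the blanked values.

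The other sensitivity analysis in SAP 9.3, for missing data in the mITT analysis, does distinguish arms: "missing data from discontinuations in the arm found to be superior will be imputed based on data from the less superior arm".

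**The concern.** A tipping-point analysis should show how bad the unseen outcomes would have to be before the conclusion fails. If every imputed value in both arms is worsened by the same amount, the two arms' means move in the same direction and part or all of the stress is lost from their difference. How much is lost depends on the split of imputed values between arms, which is not known in advance. A large tipping value, or none at all, could then be reported as robustness when it reflects how the shift was applied.

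This analysis may carry more weight than its supportive label suggests. The control-based analysis of the mITT result runs only if more than 10% of 6-month scores are missing and a group difference is seen (SAP 7.3 and 9.3). The plan expects 5% discontinuation by 6 months (SAP 6), and the mITT analysis keeps scores recorded after off-protocol treatment (SAP 7.4). On those assumptions the control-based analysis would not be triggered. The tipping-point analysis has no such trigger and could be the only check made under a not-missing-at-random assumption.

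**Working it through.** **Inputs from the SAP.** SD 46.5, target difference 26, 69 evaluable women per arm and 90% power (section 6); two-sided 0.05 (section 7.8).

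**Assumptions.** The documents give no rate of off-protocol treatment by arm; Protocol 3.4.1.c expects only that it will be low. Imputed shares of 5% to 15% per arm and an observed difference of 20 points are illustrative.

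**The plan's own figure.** The planned SE is 46.5 × √(2/69) = 7.9. A two-sample t calculation with 69 per arm and a difference of 26 gives 90.3% power, which agrees with the stated 90%. Also 69/0.95 = 72.6, hence 73 randomized per arm.

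**Formulas.** Let D be the advantage of the better arm, f_b and f_w the imputed shares in the better and worse arms, and δ_b and δ_w the shifts.

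- Shifted difference: D′ = D − δ_b·f_b + δ_w·f_w. With a common shift δ this is D − δ(f_b − f_w).
- Variance: the sum over the two arms of SD²/[n(1−f)] + f(1−f)δ²/n. The first term approximates the information lost to imputation. The second is the spread added by shifting a fraction f of the arm.
- The result tips when D′/√variance falls below 1.978 (t, 136 degrees of freedom).

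**Equal shares, 10% and 10%.**

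- Common shift of 112: D′ = 20. Variance = 2 × [2162.25/62.1 + 0.09 × 12544/69] = 2 × (34.82 + 16.36) = 102.4, so SE = 10.12, t = 1.977 and p ≈ 0.05.
- Better arm only, shift of 34: D′ = 20 − 3.4 = 16.6, SE = 8.43, t = 1.97 and p ≈ 0.05.

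**More imputed in the worse arm, 15% against 5%.**

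- Common shift of 118: D′ = 20 − 5.9 + 17.7 = 31.8, SE = 10.26 and p ≈ 0.002. The advantage has grown.
- Common shift of 300: D′ = 50, SE = 17.3 and p ≈ 0.004. The UDI total is the sum of three subscales scored 0 to 100 (SAP 9.2), so 300 is the whole scale.
- Better arm only, shift of 64: D′ = 16.8, SE = 8.52 and p ≈ 0.05.

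**Tipping values in points**

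| Imputed share, worse / better arm | D = 20: common | D = 20: better arm only | D = 26: common | D = 26: better arm only |
|---|---|---|---|---|
| 5% / 5% | 163 | 71 | 279 | 159 |
| 10% / 10% | 112 | 34 | 199 | 85 |
| 15% / 15% | 88 | 20 | 164 | 56 |
| 5% / 15% | 32 | 23 | 78 | 59 |
| 15% / 5% | none to 300 | 64 | none to 300 | 154 |

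**Check by simulation** (two-sample multiple imputation, 600 imputations, D = 20).

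- 10%/10%: p goes from 0.016 to 0.042 at a common shift of 100, and to 0.28 when only the better arm is shifted by 100.
- 15% worse, 5% better: p falls from 0.017 to 0.002 under the common shift.
- 5% worse, 15% better: a common shift of 40 already gives p = 0.066.

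These are two-sample approximations, not the planned repeated-measures model.

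**Scale.** The mean improvement in the sling-only group of the earlier mixed-incontinence trial was 114.7 points (Protocol 2.1.1). A tipping value of 112 thus removes nearly all of an average response; a value of 34 removes less than a third (34/114.7 = 30%).

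**The case against.** Five points can be made for the plan.

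1. **The text does not say both arms.** This stands. A common shift is the natural reading of two sections that describe a single series and name no arm, but it is not stated. If something else was meant, the same clarification is needed.

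2. **A tipping point exists even with equal shares.** This stands. A reader might infer that no shift could ever overturn the result when shares are equal. The documents do not support that: the criterion is the p-value, and the added variance raises it even though the estimate stays put. What remains is that the tipping value is about 2 to 4 times the better-arm-only value at D = 20.

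3. **The shift does not cancel in general.** This stands too. A reader might infer that cancellation is a general property of the method. It needs similar shares, and if the better arm has more imputed values most of the stress survives. The reverse imbalance, however, is worse than cancellation, because the shift then favours the better arm. Protocol 3.4.1.a raises, as a hypothetical, that women given Botox A might ask for more additional treatment. If Botox A were also the weaker arm, that case would apply.

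4. **A common shift fits the stated worry, which applies to both arms.** This is partly right. No passage shows that the worsening would differ by arm. But a robustness claim should also cover unequal worsening, and SAP 9.3 already penalises only the superior arm in its control-based analysis.

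5. **Only a supportive analysis is involved, and additional treatment will be compared by arm (SAP 9.4).** This is correct, and it limits the point. The comparison lets a reader see an imbalance but does not supply the missing arm-specific result.

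**Conclusion.** The point holds in a limited form. SAP 7.4 and 9.3 give one series of fixed worsening amounts without distinguishing arms. Followed literally, the analysis can overstate robustness when imputed shares are similar (about 112 against 34 points at 10%/10%). It can strengthen the result it is meant to test when the worse arm has more imputed values (no tipping up to 300 points, against 64). It works reasonably when the better arm has more (32 against 23). These figures assume an observed difference of 20, 69 per arm, SD 46.5 and the stated shares; the pattern is the same at a difference of 26. The actual shares by arm are not in the documents, so which case applies is unknown.

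A reader might infer that the trial's main conclusion is at risk. It is not: the primary mITT test and its control-based sensitivity analysis do not use this rule. The plan should nevertheless be changed, because the tipping-point result would be read as evidence of robustness.

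**What to change.** In SAP 7.4 and 9.3, define the tipping-point analysis with a separate shift for each arm on a two-way grid. Include the edge where only the arm that appears better is shifted, which matches the logic of the control-based analysis in the same section. State the step and the range, and say whether values missing from ordinary missed visits are shifted as well as those blanked after off-protocol treatment. Report the pairs of shifts at which the 6-month conclusion changes, together with the number of 3- and 6-month values set to missing in each arm. The equal-shift diagonal of the grid keeps the analysis as it now reads.

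The cost is more imputation runs and a slightly larger display. No new data are needed.
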